STUDY PROTOCOL AND STATISTICAL ANALYSIS PLAN

Official Title:

Dynamic Magnesium Replacement Strategies and 28-Day Mortality in Non-Cardiac Critically Ill Patients: A Target Trial Emulation Study

Date: December 24, 2025

Principal Investigator: [name]., Ph.D.

Study Type: Observational (Retrospective Cohort)

SECTION 1: STUDY PROTOCOL

1. Study Identification

Brief Title:

Magnesium Replacement Strategies in Non-Cardiac ICU Patients

Official Title:

Dynamic Magnesium Replacement Strategies and 28-Day Mortality in Non-Cardiac Critically Ill Patients: A Nonrandomized Clinical Trial using Target Trial Emulation

Study Design:

Observational, Retrospective, Cohort Study.

2. Study Status

Overall Status: Completed (Retrospective analysis of existing data).

Study Start Date: September 2025 (Analysis start).

Primary Completion Date: December 2025.

Study Completion Date: December 2025.

3. Study Description

Brief Summary:

This study evaluates the association between different dynamic magnesium replacement strategies and 28-day all-cause mortality in non-cardiac critically ill patients with hypomagnesemia. Using data from the MIMIC-IV database, the study employs a target trial emulation framework (G-formula) to simulate and compare three strategies: 'Never Treat', 'Always Treat', and 'Dynamic Treat' (treat only when hypomagnesemic).

Detailed Description:

Magnesium supplementation is common in the ICU, but evidence for its mortality benefit in non-cardiac patients is lacking. This study aims to fill the gap by emulating a randomized controlled trial using observational data. We utilize the Medical Information Mart for Intensive Care IV (MIMIC-IV) database. We define 'Time Zero' as the first occurrence of hypomagnesemia (<1.7 mg/dL) within 72 hours of ICU admission. We apply the parametric G-formula to adjust for time-varying confounding affected by prior treatment, a method superior to conventional regression for dynamic treatment regimes. The study aims to inform clinical guidelines regarding the necessity and safety of routine magnesium repletion.

4. Study Design

Observational Model: Cohort.

Time Perspective: Retrospective.

Target Follow-Up Duration: 28 Days.

Biospecimen Retention: None.

5. Groups / Cohorts

Since this is a target trial emulation, the "Groups" are hypothetical strategies defined by the analysis as follows:

Group 1: Never Treat Strategy

Description: A simulated strategy where patients receive no magnesium supplementation throughout the 28-day follow-up, regardless of serum magnesium levels.

Group 2: Always Treat Strategy

Description: A simulated strategy where patients receive daily magnesium supplementation throughout the 28-day follow-up.

Group 3: Dynamic Treat Strategy

Description: A simulated strategy where magnesium supplementation is administered on a given day only if the daily serum magnesium level falls below 1.7 mg/dL.

Reference: Natural Clinical Course (Observed data).

6. Eligibility Criteria

Study Population: Adult patients admitted to the ICU in the MIMIC-IV database (2008-2019).

Inclusion Criteria:

1. Age \geq 18 years.
2. Admitted to the Intensive Care Unit (ICU).
3. Developed hypomagnesemia (Serum Magnesium < 1.7 mg/dL) within the first 72 hours of ICU admission.

Exclusion Criteria:

1. Admitted due to cardiac or cardiosurgical causes (e.g., Cardiac Surgery Recovery Unit, CCU, CVICU).
2. Underwent cardiac surgery during hospitalization (identified by ICD-9/10 procedure codes).
3. Primary discharge diagnosis of major cardiac conditions (e.g., myocardial infarction, heart failure, arrhythmias).

7. Outcome Measures

Primary Outcome Measure:

1. 28-Day All-Cause Mortality

Description: Cumulative incidence of death from any cause within 28 days from inclusion (Time Zero).

Time Frame: 28 days.

Secondary Outcome Measures:

1. Risk Difference (RD)

Description: The absolute difference in mortality risk between the emulated strategies (Never/Always/Dynamic) and the natural clinical course or between strategies.

Time Frame: 28 days.

2. Number Needed to Treat (NNT)

Description: Calculated to estimate the number of patients needed to be managed under a specific strategy to avert one death.

Time Frame: 28 days.

SECTION 2: STATISTICAL ANALYSIS PLAN (SAP)

1. Analysis Dataset

Source: MIMIC-IV database (version 3.1).

Data Structure: Longitudinal dataset with a daily time-grid (days 0 to 27) relative to Time Zero (T0).

Missing Data Handling: Last Observation Carried Forward (LOCF) will be used for time-varying covariates.

2. Variables

Exposure (Treatment): Magnesium replacement therapy (binary variable per day: administered yes/no).

Baseline Covariates: Age, Gender, Charlson Comorbidity Index (CCI).

Time-Varying Covariates (Daily):

Laboratory: Serum magnesium, Hemoglobin, Creatinine, Arterial pH.

Vitals/Scores: Mean Blood Pressure (MBP), SOFA score.

Therapeutics: Vasopressor use (binary).

Outcome: Death (binary).

Competing Event: Live discharge from ICU.

3. Statistical Methodology: The G-Formula

To estimate the causal effect of dynamic magnesium strategies while accounting for time-varying confounding affected by prior treatment (feedback loops), the parametric G-formula will be employed.

Step 1: Parametric Modeling

Pooled parametric regression models will be fitted for:

- The outcome (Death).
- The competing event (Live discharge).
- Each time-varying covariate (Mg, Hb, Cr, pH, MBP, SOFA, Vasopressors).

Model Specifications: Models will include lagged values, cumulative averages, and non-linear quadratic terms for continuous variables to capture complex dependencies. An interaction term between Magnesium Treatment and SOFA score will be included.

Step 2: Monte Carlo Simulation

A random sample of 5,000 subjects (bootstrapped) will be used for simulation.

We will simulate the 28-day trajectory of the cohort under the three specific interventions (Never Treat, Always Treat, Dynamic Treat) by setting the treatment variable according to the rule of each strategy and predicting subsequent covariates and outcomes based on the fitted models.

Step 3: Effect Estimation

Cumulative Risk: Calculated for mortality at Day 28 for each strategy.

Comparisons: Risk Difference (RD) and Risk Ratio (RR) will be calculated comparing 'Always Treat' and 'Dynamic Treat' against 'Never Treat' (Reference).

Inference: 95% Confidence Intervals (CIs) will be derived using non-parametric bootstrapping with 1,000 resamples.

4. Sensitivity Analyses

To verify the robustness of the G-formula models, the following analyses will be performed:

1. Simplified Models: Re-running the analysis using linear models for all covariates (excluding quadratic terms).
2. No Interaction Models: Re-running the analysis excluding the treatment-by-SOFA score interaction term.
3. E-value Calculation: To assess the potential impact of unmeasured confounding on the observed Risk Ratio.

5. Subgroup Analyses

Treatment effects will be evaluated across the following baseline subgroups:

1. Hypomagnesemia Severity: Severe vs. Mild (dichotomized by median).
2. Renal Function: Creatinine ≥ 1.2 vs. < 1.2 mg/dL.
3. Hemodynamic Status: Vasopressor use vs. None.
4. SOFA Score: ≥ 8 vs. < 8 .
5. Age: ≥ 65 vs. < 65 years.

Interaction p-values between subgroups will be estimated via bootstrap-based covariance correction.

6. Software

All analyses will be performed using R (version 4.3.1) and the 'gfoRmula' package. A two-sided p-value < 0.05 will be considered statistically significant.

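### Exclusion 2 removes patients for cardiac surgery that may happen after Time Zero; Exclusion 3 may do the same, depending on how discharge diagnoses are coded

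*Combined protocol and SAP*

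**What the plan says.** Protocol section 3 fixes the start of follow-up: "We define 'Time Zero' as the first occurrence of hypomagnesemia (<1.7 mg/dL) within 72 hours of ICU admission". Protocol section 7 counts the primary outcome from the same point: "Cumulative incidence of death from any cause within 28 days from inclusion (Time Zero". The SAP's daily grid (section 1, days 0 to 27) also runs from Time Zero.

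Protocol section 6 lists three exclusions:

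- Exclusion 1: "Admitted due to cardiac or cardiosurgical causes (e.g., Cardiac Surgery Recovery Unit, CCU, CVICU". This is tied to the admission, so as worded it is known by Time Zero.
- Exclusion 2: "Underwent cardiac surgery during hospitalization (identified by ICD-9/10 procedure codes". The window is the whole hospital stay.
- Exclusion 3: "Primary discharge diagnosis of major cardiac conditions (e.g., myocardial infarction, heart failure, arrhythmias". This label is assigned at the end of the stay.

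Neither document limits Exclusion 2 or 3 to information available at Time Zero. SAP section 4 plans three sensitivity analyses: "Re-running the analysis using linear models for all covariates (excluding quadratic terms"; "Re-running the analysis excluding the treatment-by-SOFA score interaction term"; and an E-value, "To assess the potential impact of unmeasured confounding on the observed Risk Ratio". None of them changes who is in the cohort.

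**The concern.** In the randomized trial being emulated, eligibility would be settled at Time Zero, before anyone could know about later surgery or later cardiac events. Exclusion 2 uses such later information. A patient who dies early cannot meet it through subsequent surgery, so that part of the rule removes only people who survived long enough to be operated on. By then the daily magnesium exposure is already running.

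The primary outcome is death from any cause, so patients with later surgery belong in follow-up. If magnesium affects the events that lead to removal (an assumption; the documents are silent), the comparison of strategies is open to selection bias. The G-formula cannot undo this, because its models are fitted after exclusion and the removed patients supply no data. If magnesium does not affect those events, a null contrast stays null, and what changes is the absolute risk and the population it describes.

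**Working it through.** **Timing of each rule against Time Zero**

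| Rule | Information used | Can it postdate Time Zero? |
|---|---|---|
| Exclusion 1 | Cause of admission, ICU unit type | Not as worded |
| Exclusion 2 | Cardiac surgery at any point in the stay | Yes |
| Exclusion 3 | Primary diagnosis assigned at discharge | Only if a later event is coded as primary; not described |

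The documents give no count per exclusion, no event timing and no event rate. There is therefore no figure of the plan's to reproduce, and every input below is assumed.

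**Exclusion 2: shift in absolute risk**

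Let *s* be the share who would have cardiac surgery after Time Zero. Of these, 5% die first and are kept; the other 95% are removed, and a proportion *x* of the removed die by day 28. Everyone else dies at 15%.

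- Full-cohort risk = s(0.05 + 0.95x) + (1 - s)(0.15)
- Risk after exclusion = [0.05s + 0.15(1 - s)] / [0.05s + (1 - s)]
- Shift = risk after exclusion minus full-cohort risk, which simplifies to 0.95s × (risk after exclusion - x)

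For s = 1%, x = 10%: full risk is 0.01 × 0.145 + 0.99 × 0.15 = 14.995%. After exclusion it is 0.149/0.9905 = 15.043%. The shift is +0.048 points.

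| s | Risk after exclusion | Full risk, x = 10% | Shift | Full risk, x = 25% | Shift |
|---|---|---|---|---|---|
| 1% | 15.043% | 14.995% | +0.05 | 15.137% | -0.09 |
| 3% | 15.131% | 14.985% | +0.15 | 15.412% | -0.28 |
| 5% | 15.223% | 14.975% | +0.25 | 15.687% | -0.46 |

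(The first x = 25% shift is -0.095 to three decimals.) The sign changes where x equals the risk after exclusion, about 15%. If treatment multiplies all these death risks by 0.9 and leaves *s* alone, the risk ratio is 0.900 both before and after exclusion.

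**Later cardiac events that lead to exclusion (mainly Exclusion 3)**

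Let *c*, from 0.1 to 1.0, be the share of later events that lead to removal.

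*True null on death with an unmeasured shared cause.* The cause is present in 30%. Death is 30% with it and 10% without it, so true risk is 16.0% under both strategies. Event risk is three times higher with the cause, and treatment multiplies event risk by 0.6. At 10% event risk overall, the untreated event risks are 18.75% and 6.25%, and the treated ones 11.25% and 3.75%. With c = 1:

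- Untreated: (0.3 × 0.8125 × 0.3 + 0.7 × 0.9375 × 0.1)/0.90 = 15.417%
- Treated: (0.3 × 0.8875 × 0.3 + 0.7 × 0.9625 × 0.1)/0.94 = 15.665%
- Spurious RD +0.25 points, RR 1.016

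Over the range of *c*, the spurious RD is +0.004 to +0.04 points at 2% event risk, +0.01 to +0.11 at 5% and +0.02 to +0.25 at 10%. With no treatment effect on the event it is zero throughout.

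*Effect running wholly through the event.* Risk after exclusion = [p(1 - c)d1 + (1 - p)d0]/(1 - cp), where *p* is event risk, d1 = 0.40 is death with the event and d0 = 0.15 without it. At 5% v 3% event risk, the true RD of -0.50 points becomes -0.45 (c = 0.1) to 0.00 (c = 1). At 10% v 6%, -1.00 becomes -0.91 to 0.00.

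*Opposing effects that cancel exactly.* If d0 under treatment is raised so that the true RD is zero (0.1606 at 10% v 6%), the spurious RD runs from +0.09 to +1.06 points. The last figure needs every event to be excluded.

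**The case against.** The best defence is that the certain part of the problem is small and the larger figures are speculative. Only Exclusion 2 demonstrably reaches past Time Zero, and its illustrated effect is under half a point of absolute risk. A primary discharge diagnosis will often reflect the reason for admission, so Exclusion 3 mainly does what a study of non-cardiac patients needs. This stands, and it is why Exclusion 3 is only a conditional concern here. It does not rescue the Exclusion 2 window, and only counts could show that the effect is negligible; the plan provides for none.

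A second objection also stands: correcting Exclusion 2 brings back patients who have cardiac surgery during follow-up, and surgery is not among the time-varying covariates in SAP section 2. If surgery changes both later magnesium use and death (an assumption), unmodelled confounding enters. The fix has to address this.

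A reader might infer that Exclusion 3 is as clearly wrong as Exclusion 2, or that the reported strategy effects are biased by a known amount in a known direction. The documents support neither. They do not say how often a later event becomes the primary diagnosis. They give no event rate and no effect of magnesium on such events, and the sign of the Exclusion 2 shift turns on a mortality figure they do not contain.

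**Conclusion.** Exclusion 2 is wrong as written for a target trial emulation: it lets eligibility depend on surgery after the start of follow-up. Confidence in that textual finding is high. Surgery already performed by Time Zero is a legitimate ground for exclusion. Exclusion 3 warrants counts and a sensitivity cohort, not a finding of error.

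The consequence is uncertain and, under the assumed inputs, small to moderate. For Exclusion 2 the absolute-risk shift could have either sign. The risk ratio is preserved only if treatment does not change surgery and acts by the same ratio in all patients. For later cardiac events, selection bias in the contrast requires treatment to affect those events. With a shared unmeasured cause and a true null, it reaches at most +0.25 points under the inputs used. Larger distortions need the treatment effect to run through the event, or opposing effects to cancel. The point should be fixed, but it does not by itself invalidate the study.

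**What to change.** 1. Limit Exclusion 2 to cardiac-surgery procedures dated at or before Time Zero. If dates are not available, report results with and without Exclusion 2.
2. Report how many patients each exclusion alone removes, and how many of the surgeries are dated after Time Zero.
3. Add one sensitivity cohort in which non-cardiac status is defined only from information available by Time Zero (ICU unit type and, where held, admitting service or admission reason), without Exclusion 3. Report it beside the main cohort whatever it shows; the results should not decide which cohort carries the conclusion.
4. Add cardiac surgery during follow-up as a time-varying covariate where it is dated, or state as a limitation that it is not modelled.
5. Label the change post hoc, since Protocol section 2 lists the study as completed.

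Cost: rewording Exclusion 2 changes the main cohort. The main analysis with its 1,000 bootstrap resamples, the subgroups and the sensitivity analyses must all be re-run, plus one run in the added cohort. All of this uses existing data, although the documents do not confirm that procedure dates, admitting service or admission reason are held. There are two downsides: patients with later surgery stay in the main cohort, and some patients admitted to a general ICU for a cardiac reason may enter the sensitivity cohort.

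### Comfort-care status is neither excluded nor recorded, so the contrasts with Never Treat are likely to be biased towards treatment, by an unknown amount

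*Combined protocol and SAP*

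**What the plan says.** - **Entry (Protocol 6).** A patient qualifies on "Developed hypomagnesemia (Serum Magnesium < 1.7 mg/dL) within the first 72 hours of ICU admission". Nothing is required about goals of care.
- **Exclusions (Protocol 6).** There are three: "Admitted due to cardiac or cardiosurgical causes (e.g., Cardiac Surgery Recovery Unit, CCU, CVICU", "Underwent cardiac surgery during hospitalization (identified by ICD-9/10 procedure codes" and "Primary discharge diagnosis of major cardiac conditions (e.g., myocardial infarction, heart failure, arrhythmias". All are cardiac.
- **Exposure (SAP 2).** "Magnesium replacement therapy (binary variable per day: administered yes/no". The reason for a day without magnesium is not recorded.
- **Covariates (SAP 2).** "Baseline Covariates: Age, Gender, Charlson Comorbidity Index (CCI". The daily covariates are magnesium, hemoglobin, creatinine, pH, mean blood pressure (MBP), SOFA and vasopressor use. None records code status.
- **Missing values (SAP 1).** "Last Observation Carried Forward (LOCF) will be used for time-varying covariates".
- **Leaving the risk set (SAP 2).** Besides death, the only exit is live ICU discharge, handled as a competing event. Protocol 7 defines the outcome as any death within 28 days of Time Zero.
- **Checks (SAP 4).** Two analyses change the form of the models. The third is "E-value Calculation: To assess the potential impact of unmeasured confounding on the observed Risk Ratio".

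**The concern.** The G-formula removes time-varying confounding only for what is measured. A move to comfort care is a plausible common cause of two things the models see: no magnesium that day, and death soon after. Where sampling stops, carried-forward pH, creatinine, magnesium and laboratory parts of SOFA stay at their values from before the change. The death model then meets an untreated patient, apparently no sicker than before, who dies. Withdrawal of a vasopressor would even look like improvement.

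The contrasts exposed are the main ones: Always Treat and Dynamic Treat against Never Treat. The plan also reports a number needed to treat and means to inform guidelines on routine repletion (Protocol 3). A false benefit would go straight into that conclusion.

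**Working it through.** The documents give no mortality, sample size or CMO frequency, so there is no figure of the plan to reproduce. The check asks which way the bias runs, and how large it could be, when magnesium truly does nothing.

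**Assumed inputs (none from the documents).** A 28-day daily chain with two ICU states, full care (F) and CMO (C). Each day runs: new CMO orders, magnesium, death, live discharge. Daily magnesium is p_F = 0.40 and p_C = 0.03. Daily death in CMO is h_C = 0.35. Daily ICU discharge is 12% from full care and 0 from CMO. There is no severity covariate. Daily CMO onset is set so that 0.8%, 2.0% or 4.1% of patients are ever CMO.

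**Step 1: daily death in full care.** For 28-day full-care mortality M, M = h_F(1 − q^28)/(1 − q), with q = (1 − h_F) × 0.88.
- M = 20%: h_F = 0.02956, q = 0.8540, q^28 = 0.012, and 0.02956 × 0.988/0.1460 = 0.200.
- M = 3.5%: h_F = 0.00445, q = 0.8761, q^28 = 0.025, and 0.00445 × 0.975/0.1239 = 0.035.

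**Step 2: death risk seen by a model without CMO status.**
Treated: h₁ = (F·p_F·h_F + C·p_C·h_C)/(F·p_F + C·p_C). Untreated: the same with 1 − p_F and 1 − p_C.

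First day, M = 20%, 4.1% ever CMO (onset 0.627% per day, so F = 0.99373 and C = 0.00627):
- Treated: (0.011750 + 0.000066)/(0.39749 + 0.00019) = 0.0297.
- Untreated: (0.017625 + 0.002129)/(0.59624 + 0.00608) = 0.0328.

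Within each state the true risks are equal, yet the pooled ratio is 0.0297/0.0328 = 0.91. It moves further from 1 as CMO patients accumulate.

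**Step 3: 28-day risk under each strategy.** R_a = Σ S_a(t)·h_a(t), with S_a(t+1) = S_a(t)(1 − h_a(t))(1 − d_a(t)). Here d_a is the pooled discharge probability, formed in the same way as h_a.

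| Full-care 28-day mortality | Ever CMO | Always | Never | False RR |
|---|---|---|---|---|
| 3.5% | 0.8% | 3.56% | 4.73% | 0.75 |
| 3.5% | 2.0% | 3.65% | 6.56% | 0.56 |
| 3.5% | 4.1% | 3.81% | 9.68% | 0.39 |
| 20% | 0.8% | 20.05% | 21.03% | 0.95 |
| 20% | 2.0% | 20.12% | 22.55% | 0.89 |
| 20% | 4.1% | 20.26% | 25.16% | 0.81 |

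**Step 4: what moves the result.** A second null chain assumes, in full care, 1% daily death, 12% discharge and 50% magnesium. CMO onset is 1% per day (about 7% ever), with 5% daily magnesium and 50% daily death in CMO.
- No ICU exit from CMO: 8.3% versus 19.7%, RR 0.42.
- Adding a severity marker that detects CMO with 95% sensitivity and 2% false positives: RR 0.54.
- Milder case (onset 0.5%, magnesium 25%, death 20%, ICU exit 60% per day): RR 0.91.
- Equal magnesium in and out of CMO, or CMO status in the models: RR 1.00.
- All CMO patients leave the ICU alive the same day and count as discharged: 7.55% versus 6.68%, RR 1.13.
- CMO patients who do not die leave the same day: the null is crossed at a daily CMO death risk of about 8%.
- Magnesium given more often in CMO (70%), no ICU exit: 16.8% versus 11.8%, RR 16.8/11.8 = 1.42.

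**Step 5: the E-value.** For RR 0.80, 1/0.80 = 1.25 and E = 1.25 + √(1.25 × 0.25) = 1.81. This says how strong a confounder would have to be. It adjusts for nothing.

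**The case against.** The strongest reply has four parts.

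1. **Direction.** A reader might infer that the bias must favour treatment. The documents do not support that. Live ICU discharge removes patients from the risk set, and if a later death on a ward or in a hospice is not counted, stopping magnesium at the change of goals makes Never Treat look safer (RR 1.13 above). This stands: the direction is likely, not certain.
2. **Size.** A reader might infer that a CMO share under 1% is enough for a large false benefit. That depends on baseline mortality, which the documents do not give. At 0.8% ever CMO the RR is 0.75 with 3.5% full-care mortality and 0.95 with 20%. This stands too.
3. **Adjustment.** The plan's models are richer than these chains. They include MBP and vasopressors, which may still be charted after sampling stops, as well as pH, SOFA and cumulative averages. Some confounding would be absorbed, so it is too strong to say that these covariates cannot help. But even a very accurate marker moved the RR only from 0.42 to 0.54, so absorption is likely to be incomplete.
4. **Entry.** A measured low magnesium is needed to enter, so few patients already in comfort care may qualify if blood draws stop there. This stands: a Time Zero exclusion alone would do little, because most of the bias arises from later transitions.

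None of this supplies the missing variable. A sign that depends on an unrecorded process is a reason to record it.

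**Conclusion.** The omission is plain on the page: comfort-care status is not excluded, measured, censored or examined. Run as written, the plan leaves a potentially strong time-varying confounder unadjusted. Bias towards Always Treat and Dynamic Treat is likely, provided that magnesium is usually stopped after the change and that such patients mostly die in the ICU. Both are assumptions.

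The size is unknown. The table's RRs, from 0.39 to 0.95, show what is possible under stated inputs and do not predict this study's result. They cover Always versus Never only. Dynamic Treat treats on a subset of days and should be affected in the same direction, but it was not computed. The documents do not support a claim that a false benefit will appear, or that the bias can run only one way.

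**What to change.** 1. **Main correction.** Add a daily code-status or CMO variable to the time-varying covariates in SAP 2, ordered before that day's magnesium. Give it its own model in Step 1 and use it as a predictor in the death and discharge models. Report the number of treated CMO days; if there are few, Always Treat is an extrapolation there.
2. **Entry.** Exclude patients with a CMO order at or before Time Zero, and limit the conclusion to patients receiving full ICU care at entry.
3. **Sensitivity analysis.** Censor at transition to CMO, with weights, and state that this changes the estimand.
4. **Outcome.** State in SAP 2 that deaths after live ICU discharge count towards the 28-day outcome, and reconcile this with the competing-event rule. This choice affects the direction of the bias.

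**Cost.** The study is listed as completed, so the models and 1,000 bootstrap resamples must be rerun on existing records. The cohort will be slightly smaller. Charting of code status will be imperfect, and its availability is an assumption. If it proves unusable, the plan should say so and limit its causal claim.

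### Where magnesium is not measured daily, LOCF can distort when the simulated Dynamic arm is treated, and no planned sensitivity analysis would show it

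*Combined protocol and SAP*

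**What the plan says.** - **Missing data (SAP 1).** "Missing Data Handling: Last Observation Carried Forward (LOCF) will be used for time-varying covariates". No limit on the length of carry-forward is given. The dataset is a "Longitudinal dataset with a daily time-grid (days 0 to 27) relative to Time Zero (T0").
- **Strategy (Protocol 5, Group 3).** "magnesium supplementation is administered on a given day only if the daily serum magnesium level falls below 1.7 mg/dL".
- **Exposure (SAP 2).** "Exposure (Treatment): Magnesium replacement therapy (binary variable per day: administered yes/no").
- **Models (SAP 3, Step 1).** A pooled regression is fitted for "Each time-varying covariate (Mg, Hb, Cr, pH, MBP, SOFA, Vasopressors"). The named terms are lags, cumulative averages, quadratics and a treatment-by-SOFA interaction. No measurement indicator or time since last measurement is named.
- **Simulation (SAP 3, Step 2).** Treatment is set by each strategy's rule, followed by "predicting subsequent covariates and outcomes based on the fitted models".
- **Contrasts (SAP 3, Step 3).** Risk differences and ratios "comparing 'Always Treat' and 'Dynamic Treat' against 'Never Treat' (Reference").
- **Sensitivity analyses (SAP 4).** There are three: no quadratic terms, no interaction, and an E-value.

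Neither part of the document says how often magnesium is measured.

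**The concern.** Magnesium is the one covariate here that also assigns treatment. In Step 2 its fitted model generates each simulated day's value, and the Dynamic rule reads that value against 1.7 mg/dL. On a carried-forward day the recorded value equals the previous one by construction, so the data appear to say that yesterday's treatment did nothing. When a measurement finally arrives, the change since the last one reflects every treatment given in between, yet the model attributes it to a single day.

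The simulated Dynamic arm may therefore be treated on a different number of days from the strategy it is meant to represent, and that arm supplies one of the two planned contrasts with Never Treat. Simulated magnesium under Always and Never is affected as well. Two of the SAP 4 analyses change model form and the third concerns unmeasured confounding. All three leave LOCF in place.

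**Working it through.** The plan gives no measurement frequency, treatment effect on magnesium or event count, so there is no figure of its own to reproduce. What follows shows the mechanism and an illustrative size.

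**Mechanism.** Let R be recorded magnesium, A treatment, b the true next-day effect and p the share of days measured. Then R_t = Mg_t on a measured day and R_(t-1) otherwise. If measurement is random and treatment is decided on recorded values, the expected R_t given the past is p × E(Mg_t) + (1 − p) × R_(t-1). The coefficient on A_(t-1) is therefore p × b. With b = 0.30 mg/dL:
- 90% measured: 0.9 × 0.30 = 0.27
- 70% measured: 0.7 × 0.30 = 0.21
- 50% measured: 0.5 × 0.30 = 0.15

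**Simulation inputs.** From the documents: the 1.7 mg/dL threshold, 28 daily steps, binary daily treatment, and lag, quadratic and cumulative-average terms. Assumed:
- Mg_t = 0.72 + 0.6 × Mg_(t-1) + 0.30 × A_(t-1) + noise, with stationary SD 0.2 and Mg below 1.7 at T0;
- observed treatment probability 0.70 if recorded Mg is below 1.7, otherwise 0.15;
- a linear model with normal errors for magnesium;
- 20,000 patients, mean of 5 seeds.

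**Dynamic treated days out of 28**

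| Measurement pattern (assumed) | LOCF | Truth, known daily | Truth, last recorded | LOCF minus daily | LOCF minus last |
|---|---|---|---|---|---|
| Random 90% | 4.70 | 4.59 | 4.75 | +0.11 | −0.05 |
| Random 70% | 4.96 | 4.59 | 5.17 | +0.37 | −0.21 |
| Random 50% | 5.35 | 4.59 | 5.82 | +0.76 | −0.47 |
| Less after treatment (60% vs 95%) | 5.43 | 4.59 | 6.36 | +0.84 | −0.93 |
| More after treatment (95% vs 60%) | 4.27 | 4.59 | 3.92 | −0.32 | +0.35 |
| More after a low value (95% vs 60%) | 4.31 | 4.59 | 3.92 | −0.28 | +0.39 |

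With every day measured, LOCF and truth agree apart from simulation noise. In each row above, LOCF lies between the two readings and equals neither.

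**ICU exit.** SAP 2 lists "Competing Event: Live discharge from ICU", so patients leave the risk set. With an assumed 10% daily exit:
- at 70% measured, LOCF gives 2.21 against 2.07 (known daily) and 2.41 (last recorded), differences of +0.14 and −0.20;
- at 50%, it gives 2.37 against 2.07 and 2.80, differences of +0.30 and −0.43.

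**Other inputs.** With autoregression 0.4 or 0.8, or b = 0.15, LOCF missed the last-recorded truth by 0.03 to 1.20 days and the daily-known truth by 0.03 to 1.49.

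**Always minus Never, mean magnesium.** The long-run gap is 0.30 / (1 − 0.6) = 0.75. Averaged over days 1 to 27 it is 0.75 × (1 − 1.5/27) = 0.71. LOCF gave 0.69, 0.64 and 0.58 at 90%, 70% and 50% random measurement, 0.52 with less measurement after treatment and 0.81 with more.

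**Does the proposed analysis help?** Modelling measurement and simulating it gave 4.74, 5.16 and 5.79 under random measurement, and 6.32, 3.92 and 3.92 in the last three rows. All are close to the last-recorded truth. Setting the indicator to measured gave 4.59 to 4.61 under random measurement, but 4.57 to 4.84 in a second coding of the model, against 4.59. It is therefore only approximate.

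**Where it falls short.** If measurement depends on current magnesium that went unrecorded (95% if below 1.7, otherwise 60%), it gives 5.82 and LOCF 5.53, against 6.36. If the true effect varies with magnesium level (1.3 times below 1.7, 0.7 times above), both methods give about 4.57 against 4.23 even with daily measurement.

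**The case against.** The strongest defence is that the last recorded value is what clinicians saw. It may then be the right confounder for treatment, and 0.27, 0.21 and 0.15 are correct effects on the next recorded value rather than attenuated ones. This stands: the shrunken coefficient is bias only if the rule means magnesium known daily. It does not rescue the planned model, which also misses the last-recorded truth because it leaves out when measurement happens.

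Second, every size above rests on assumed inputs, concerns treated days rather than deaths, and shrinks with ICU exit. This stands too, and it limits the claim.

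Third, a reader might infer that Group 3 contradicts SAP 1, or that the simulated arm meets days without a value. Neither follows. Step 2 predicts magnesium on every simulated day, and SAP 1 supplies a value for every day in the data. What is unclear is which strategy those values represent.

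A reader might also infer that LOCF can overstate the next-day treatment effect. In the three patterns of informative measurement that coefficient was 0.18 to 0.26, below 0.30 throughout. Only the accumulated Always-minus-Never contrast came out too large, and only under some patterns.

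**Conclusion.** The concern holds in a limited form. If magnesium is not measured daily, the planned LOCF-fitted model represents neither reading of the Dynamic rule, and nothing in SAP 4 would reveal it. For the daily-known reading the next-day effect is attenuated. For the last-recorded reading the fault is the missing measurement process, and the direction of error depends on that process.

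Under the base inputs the shift is modest: about 0.1 to 0.8 treated days of 28 under random measurement at 90% to 50%, and up to about 0.9 when measurement depends on prior treatment. If magnesium was measured on nearly every patient-day, the point largely closes.

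A reader might go further and conclude that the mortality comparison is biased, or biased in a known direction. The documents do not support that. They give neither the measurement pattern nor the link from treated days to death, so no effect on 28-day mortality can be derived.

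**What to change.** Keep LOCF in the primary analysis.

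1. **Report measurement.** Give the share of patient-days with a measured magnesium, overall and on the day after a treated versus an untreated day, and the distribution of carry-forward length.
2. **Add one sensitivity analysis to SAP 4.** Protocol 2 lists the study as completed, so label it as added after completion.
   - Model a daily indicator for magnesium measured.
   - Fit the magnesium model on measured days only, adding time since, and treated days since, the last measurement.
   - Simulate the indicator, and carry magnesium forward on simulated unmeasured days.
   - Report the Dynamic and Always versus Never risk differences with 95% CIs beside the LOCF results, and qualify the conclusion if they differ materially. State before the run what counts as material. A change of sign or a CI crossing zero is a poor test alone, because a trivial shift near zero can trigger it.
   - Setting the indicator to measured may be shown as an approximate check of the daily-known reading.
3. **Reconcile the wording.** The sponsor should reconcile the daily level named in Group 3 with the carried-forward values in the dataset. No clinical rule is proposed here.

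**Cost.** Two extra models and one further run with its 1,000 resamples, on existing data. It needs a flag for days with an actual result. The documents do not say one was kept, but LOCF cannot be applied without knowing those days. The analysis covers magnesium only, not the other carried-forward covariates, and bias remains if measurement depends on unrecorded current magnesium.
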